8.2.2. Study conduct

The cohort study will be conducted by investigators at the University of California Research Center for the MotherToBaby/ OTIS. The OTIS organization is a network of university and health department based telephone information centers serving pregnant women and health care providers throughout the U.S. and Canada [Leen-Mitchell, 2000]. These services receive spontaneous telephone inquiries from women who are pregnant or considering pregnancy as well as from health care providers about the safety or risk associated with environmental exposures in pregnancy, including medications. Trained

Teratogen Information Specialists at each site provide appropriate risk assessment and referral for all patient and health care provider callers free of charge. These services also provide a basis for collaborative research such as this study. Thus, individual Teratogen Information Services located throughout the U.S. and Canada will serve as a primary source of referrals not only for belimumab-exposed pregnancies but also for similarly ascertained pregnant women with a diagnosis of SLE but not treated with belimumab.

Other methods of raising awareness about the study are meeting exhibits at professional practice meetings nationally, regionally and locally, direct mail to health care providers, media, social media, and website. Rheumatologists and rheumatology healthcare professionals will be a particular focus of awareness activities. Awareness activities will also be directed to maternal-fetal medicine specialists, obstetricians, primary care physicians (PCP), and other specialists caring for women with SLE.

The US and Canada's belimumab package insert contains information about the belimumab pregnancy exposure registry and encourages healthcare providers to register patients and pregnant women to register themselves by calling the study toll-free number as soon as the pregnancy is known.

In addition, members of the Scientific Advisory Board will be asked to promote recruitment among colleagues. The existing Toll Free number for North American callers currently being utilized by all MotherToBaby Pregnancy Studies and the OTIS Autoimmune Diseases in Pregnancy Project [contact]) will be maintained as a considerable amount of previous publicity for this number will enhance ease of contact for patients to the Registry.

The existing MotherToBaby/OTIS Autoimmune Diseases in Pregnancy Project contact and referral information is available on the website and multiple methods are used to increase awareness through the website (<https://mothertobaby.org/pregnancy-studies/>), social media and print advertising. The FDA website (<http://www.fda.gov/womens/registries/default.htm>) lists the MotherToBaby/OTIS Pregnancy Studies and will have this Registry added to their listing. The study will also be listed on ClinicalTrials.gov.

This information will also be made available 1) in the prescribing information (package insert) for belimumab and other product literature and promotional materials, and 2) via a link from the GSK website. Additional venues for publicizing the Registry include: 1) linking the Registry website to other specialty provider and maternal health interest websites, 2) posting notices in appropriate journals or patient advocacy publications, and 3) later, presenting Registry data at specialty provider, and obstetrics-related scientific and clinical meetings. In addition, the Registry will enlist the aid of the U.S. Food and Drug Administration (FDA), the U.S. Centers for Disease Control and Prevention (CDC), and other relevant organizations in facilitating patient recruitment, and the Sponsor will also provide information about the Registry at appropriate professional meetings. Additional venues for publicizing the Registry include advocacy groups and patient support networks. The Sponsor may facilitate awareness among prescribers through Medical Science Liaisons.

The Sponsor will encourage exposed women or their Healthcare Providers to contact the Registry directly.

Women who are interested in hearing more about the study will be referred to or will self-refer themselves to the MotherToBaby/OTIS Research Center for more information. Referrals may be by the woman's healthcare provider or by the MotherToBaby/OTIS service that the woman contacts directly. Those women who are interested and meet the study criteria as described in Section 8.2 will be invited to enroll. Women who agree to enroll will complete the oral consent process over the telephone and will then complete the initial telephone interview. Depending on the gestational timing of enrollment, subsequent telephone interviews will be conducted according to the Schedule shown in Table 5 Section 8.6.3. Follow up interviews will be conducted by telephone, and medical records for both the women and infant will be obtained and abstracted for information to validate exposures and outcomes.

The participants will reside anywhere in the U.S. or Canada. By definition, the study participants are all female, as this is a pregnancy study. The age of participants is expected to be between 18 and 45 years; however, women under the age of 18 years may enroll with parent/guardian consent, and women over the age of 45 years may also enroll.

Upon initiation of recruitment, the study is expected to continue recruitment for five years. Infant follow-up will continue for one year after the last live birth following recruitment of the last participant.

Table 1 Recruitment Timetable

	Year 1	Year 2	Year 3	Year 4	Year 5
Cohort 1 Belimumab exposed group	40	43	48	47	42
Cohort 2 Disease comparison group	--*	50	50	50	50
Exposure Case-Series	10	10	10	10	10
*Year 1: Will assess feasibility of collecting exposed group; once n=40 is attained, recruitment of comparison group will begin					

8.3. Variables

8.3.1. Exposure definitions

Belimumab-exposed cohort: Exposure is defined as any dose of belimumab for any length of time from 3 months prior to the first day of the LMP (i.e., a period of approximately 5 belimumab terminal half-lives) through the end of pregnancy, as reported by the mother and validated through medical record review (mean termination elimination half-life of 8.5 to 14.1 days, [Furie, 2008]). Belimumab exposure will be further categorized by earliest trimester of exposure (definition from <https://www.womenshealth.gov/pregnancy/youre-pregnant-now-what/stages-pregnancy>; <https://www.ucsfhealth.org/conditions/pregnancy/trimesters>). For this study, pre-conception exposure is defined as between 3 months prior to LMP to the first day of the LMP, first trimester exposure is defined as any dose from 1st day of LMP and up to 13 weeks after 1st day of LMP; second trimester is defined as >13 weeks through 26 weeks

after 1st day of LMP, and third trimester is defined as >26 weeks after 1st day of LMP. Details of varying levels of exposure and timing will be included in the Statistical Analysis Plan (SAP).

When evaluating the primary outcome of major birth defects, exposure will be defined as yes/no in either the preconception and/or first trimester of pregnancy for major birth defects as the primary outcome. However, exposure to belimumab in the second (>13 weeks through 26 weeks after 1st day of LMP) and third trimester (>26 weeks after 1st day of LMP), will be considered for those selected major birth defects that are potentially biologically plausibly related to later pregnancy exposures, e.g., craniosynostosis [Jones, 2013]. For spontaneous abortion, the exposure is defined as yes/no in the 3 months prior to LMP and/or any time in pregnancy prior to 20 weeks of gestation, for preterm delivery, the exposure is defined as yes/no in the 3 months prior to LMP and/or any time in pregnancy prior to 37 weeks, for minor birth defects, the exposure is defined as yes/no from 3 months prior to LMP through the end of the first trimester, and for the other secondary outcomes, exposure is defined as yes/no anytime in pregnancy (from 3 months prior to LMP [as defined in Section 8.3.2] to pregnancy outcome).

Gestational age is determined by an algorithm using best available information. If the first day of LMP and cycle length is known, and ultrasound measures of dating are not discrepant according to standard conventions depending on the timing of the ultrasound, the menstrual period dating will be used to calculate gestational age. If the menstrual period dating is uncertain or unknown, and an ultrasound is available, the earliest (and therefore more precise) available ultrasound dating will be used. In the event of absence of any information on dating, the delivery record best estimate of gestational age will be used.

8.3.2. Outcome definitions

Outcome definitions and details are listed in [Table 2](#).

Table 2 Primary and Secondary Outcome Definitions

Outcome	General definition	Denominator	Pregnancy involving multiples	Outcome assessment	Exposure time	Endpoints
Pregnancy Outcome (Primary)						
Major Birth Defect²	Defined and classified using the CDC coding manual [CDC 2017], reported by the mother and validated through the medical record. The CDC coding manual is utilized to classify defects reported through the ongoing population-based Metropolitan Atlanta Congenital Defects Program (MACDP) and is based on agreed-upon criteria by CDC investigators for major birth defects regardless of etiology. Infant medical records are abstracted and reviewed by the study research team leaders.	Pregnancies ending in live births	Included counted as one case if at least one infant has a birth defect.	At birth or prior [may also be detected up to 1 year of age]	3 months prior to LMP and/or first trimester	
Primary analysis (among pregnancies with at least one live births) Cohort 1: At least one malformed infant in an individual pregnancy among pregnancies ending in at least one live birth with exposure to 3 months prior to LMP and/or 1st trimester
 
Cohort 2: At least one malformed infant in an individual pregnancy among pregnancies ending in at least one live birth with no exposure to belimumab any time in pregnancy³
 
Secondary analysis (among all pregnancies excluding lost-to-follow up) Cohort 1: At least one malformed infant or fetus in an individual pregnancy among pregnancies ending in at least one live birth with exposure to belimumab 3 months prior to LMP and/or 1st trimester
 
Cohort 2: At least one malformed infant or fetus in an individual pregnancy among pregnancies ending in at least one live birth with no exposure to belimumab any time in pregnancy³

Outcome	General definition	Denominator	Pregnancy involving multiples	Outcome assessment	Exposure time	Endpoints
Pregnancy Outcomes (Secondary)						

Spontaneous abortion (SAB)
	
Defined as spontaneous pregnancy loss prior to 20 weeks' gestation (including ectopic/molar pregnancy). In this study, since women enroll after recognition of pregnancy, SABs are only identified after enrollment in clinically recognized pregnancies. This outcome is reported by the mother and validated through the medical record, where available.
	
Pregnancies
	
Included counted as one case if all multiple pregnancies ended in SAB. Pregnancy is counted as a live birth outcome if at least one pregnancy resulted in a live-born infant
	
Up to 20 weeks gestation
	
Prior to 20 weeks gestation
	
Cohort 1: SAB among all pregnancies enrolled in the study prior to 20 weeks' gestation with exposure at any time in pregnancy³ prior to 20 weeks and with at least 1 follow-up data collection point after enrollment date
 
Cohort 2: SAB among all pregnancies enrolled in the study prior to 20 weeks' gestation with no exposure at any time in pregnancy³, with at least 1 follow-up data collection point after enrollment date

Stillbirth
	
Defined as a fetal death that occurs ≥ 20 weeks' gestation.
	
Pregnancies
	
Included counted as one case if all multiple pregnancies ended in stillbirth. Pregnancy is counted as a live birth outcome if at least one pregnancy resulted in a live-born infant
	
At birth
	
3 months prior to LMP and/or any time in pregnancy³ prior to outcome
	
Cohort 1: Stillbirths among all pregnancies¹ with exposure at any time in pregnancy³;
 
Cohort 2: Stillbirths among all pregnancies¹ with no exposure at any time in pregnancy³;

Outcome	General definition	Denominator	Pregnancy involving multiples	Outcome assessment	Exposure time	Endpoints

Elective Termination
	
Defined as deliberate termination of pregnancy at any time in gestation by surgical or medical means. Reasons for elective abortions are captured and are classified as due to medical reasons or social reasons.
	
Pregnancies
	
Included counted as one case if all multiple pregnancies ended in elective termination. Pregnancy is counted as a live birth outcome if at least one pregnancy resulted in a live-born infant
	
During pregnancy
	
3 months prior to LMP and/or at any time in pregnancy³ prior to outcome
	
Cohort 1: Elective termination among all pregnancies¹ with exposure at any time in pregnancy³; Cohort 2: Elective termination among all pregnancies¹ with no exposure at any time in pregnancy³;

Preterm Delivery
	
Defined as a spontaneous or induced delivery at <37 gestational weeks, reported by the mother and validated through the medical record. Please refer to Section 8.3.1 for further description of the method for defining gestational age and therefore preterm birth.
	
Pregnancies ending in live births
	
Excluded due to inherent higher risk of preterm birth in multiple
	
At birth
	
3 months prior to LMP and/or at any time in pregnancy³ prior to 37 weeks
	
Cohort 1: Preterm delivery among pregnancies enrolled prior to 37 weeks' gestation and ending in at least one live birth, with exposure at any time in pregnancy³ prior to 37 weeks; Cohort 2: Preterm delivery among pregnancies enrolled prior to 37 weeks' gestation and ending in at least one live birth, with no exposure at any time in pregnancy³;

Outcome	General definition	Denominator	Pregnancy involving multiples	Outcome assessment	Exposure time	Endpoints
Infant Outcomes (Secondary)						
Small for Gestational Age (SGA) Infants	Defined as live born infants who are ≤10 th centile on birth weight for infant sex and gestational age will be considered small for gestational age. The U.S. Centers for Disease Control and Prevention (NCHS) [CDC, 2000] growth charts will be used for full term infants, and the Olsen growth charts will be used for preterm infants [Olsen, 2010]. The outcome of birthweight is reported by the mother and validated through the medical record.	live born infants	Excluded due to inherent higher risk of reduced birth size in multiples	At birth	3 months prior to LMP and/or at any time in pregnancy ³	Cohort 1: SGA among live born infants with exposure at any time in pregnancy ³ ; Cohort 2: SGA among live born infants, with no exposure at any time in pregnancy ³
Minor birth defect pattern	A minor birth defect is defined as a defect that has neither cosmetic nor functional significance to the child and as itemized on the study-related dysmorphology examination form (Jones, 2013). Minor defect pattern will be defined using the following two steps: 1) identify infants with at least 3 minor structural defects of any type in the belimumab-exposed group and 2) from among infants with at least 3 minor structural defects in the belimumab-exposed group, identify any 2 or more unrelated infants with the same 3 specific minor structural defects. The prevalence of each specific pattern or patterns, if any, that are identified in the belimumab-exposed infants will be identified in the unexposed SLE comparator group. As an example, if 2 infants in Cohort 1 had the following	Live born infants	Included each counted separately for definition 1 However, in the analysis of the second definition, only one infant from a twin or higher order multiple pregnancy can be qualified as a child with the same pattern of minor structural defects, due to lack of independence for this outcome between related individuals.	Any time after birth	3 months prior to LMP and/or anytime in the 1 st trimester	1) Infant with at least 3 minor defects of any type: Cohort 1: Infants ≥ 3 minor birth defects of any type identified up to among live born infants who received a dysmorphological examination, with exposure at any time in pregnancy ³ Cohort 2: Infants ≥ 3 minor birth defects of any type identified up to among live born infants who received a dysmorphological examination, with no exposure at any time in pregnancy ³ ; 2) Infants with the same 3 minor defect patterns: Cohort 1: Infants with the same pattern of 3 minor defects identified up to among live born infants with ≥ 3 minor birth defects of any type identified any time in pregnancy ³ ; Cohort 2: Infants with the same pattern of 3 minor defects identified up to among live born

Outcome	General definition	Denominator	Pregnancy involving multiples	Outcome assessment	Exposure time	Endpoints
	
minor structural defects: "hair pattern unruly", "prominent nasal bridge", and "clinodactyly 5th finger bilateral", this would constitute one specific pattern of minor structural defects. For each specific pattern identified in Cohort 1, infants in Cohorts 2 who have the same specific pattern(s) are selected to comprise the numerator for those cohorts. In infants who have more than one specific patterns of at least 3 minor structural defects, each specific pattern will qualify as its own endpoint; therefore, the infant would be counted more than once.
					
infants, with ≥ 3 minor birth defects of any type identified, with no exposure at any time in pregnancy³;

Post-natal growth deficiency
	
Defined as postnatal size at approximately 1 year of age (weight, length or head circumference) less than or equal to the 10th percentile for sex and age using National Center for Health Statistics (NCHS) pediatric growth curves, and adjusted postnatal age for premature infants if the postnatal measurement is obtained at less than 1 year of age. [CDC, 2000].
	
Live born infants
	
Excluded due to inherent higher risk of reduced birth size in multiple
	
From birth up to 1 year of age
	
3months prior to LMP and/or at any time in pregnancy³
	
Cohort 1: Post-natal growth deficiency identified up to 1 year of age among live born infants with exposure at any time in pregnancy³
 
Cohort 2: Post-natal growth deficiency identified up to 1 year of age among live born infants, with no exposure at any time in pregnancy³

Developmental concerns
	
Defined as an abnormal score within the scoring guidelines of the Ages and Stages Questionnaire (ASQ) (Squires, 2009). The ASQ is administered at 12 months of age as a screening tool for developmental milestones by parent report. The ASQ-3 will be sent electronically to the participant or, if the participant prefers, a hard copy questionnaire will be mailed for completion.
	
Live born infants
	
Included each counted separately
	
At 1 year of age
	
3months prior to LMP and/or at any time in pregnancy³
	
Cohort 1:Developmental concerns identified at 1 year of age among live born infants, with pregnancy exposure at any time in pregnancy³;
 
Cohort 2: Developmental concerns identified at 1 year of age among live born infants, with no exposure at any time in pregnancy³

Outcome	General definition	Denominator	Pregnancy involving multiples	Outcome assessment	Exposure time	Endpoints
Serious infections up to one year of age:	Defined infections requiring hospitalization identified in live born infants up to one year of age	Live born infants	Included each counted separately	From birth up to 1 year of age	3 months prior to LMP and/or at any time in pregnancy ³	
Cohort 1: Serious infections identified up to 1 year of age among live born infants, with pregnancy exposure at any time in pregnancy³;
 
Cohort 2: Serious infections identified up to 1 year of age among live born infants, with no exposure at any time in pregnancy³

¹Pregnancy outcomes include ending in live births, spontaneous abortion, elective termination, or stillbirth

²Exposure in the 2nd and 3rd trimester will be considered for those selected major birth defects that are potentially biologically plausibly related to later pregnancy exposures, e.g., craniosynostosis

³Any time pregnancy defined as any exposure from 3 months prior to LMP through the end of pregnancy (see Section 8.3.1 for details)

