8.7. Data analysis

8.7.1. Essential analysis

A stepwise approach will be used for the analysis: The initial analysis will be descriptive and unadjusted. Where numbers permit, multivariable analyses will be conducted for the primary and secondary analyses to adjust for possible confounders.

Statistical methods:

A detailed SAP will be prepared and finalized prior to the conduct of any study analysis. Patient characteristics will be summarized within each cohort for the interim and final reports.

Table 6 summarizes the exposure window for each outcome.

Table 6 Summary of Exposure Window for Each Outcome

Outcome	Exposure Window
Major Birth Defects	3 months prior to LMP to the end of the 1 st trimester
Minor Birth Defects	3 months prior to LMP to the end of the 1 st trimester
Spontaneous Abortion/Miscarriage	3 months prior to LMP to prior to 20.0 weeks' gestation
Preterm Delivery	3 months prior to LMP to prior to 37.0 weeks' gestation
Other Outcomes	3 months prior to LMP to the end of the pregnancy

For the primary endpoint, the exposure of interest is belimumab exposure in the pre-conception/first trimester period. For this study, this exposure is defined as any dose from 3 months prior to the 1st day of LMP and up to 13 weeks after the 1st day of the LMP. The primary comparison will be on the rate of major birth defects between Cohort 1 and Cohort 2 among pregnancies resulting in at least one live born infant. A point estimate of the crude (i.e. unadjusted) RR of Cohort 1 versus Cohort 2, as well as its 95% confidence intervals (CIs) will be computed.

The comparison will also be carried out within each of two strata, according to whether the woman had prenatal diagnostic testing, such as level II ultrasound, amniocentesis or chorionic villus sampling, prior to enrollment in the study or not.

The same analysis will be repeated using the second numerator and denominator encompassing pregnancies ending in at least one live births, stillbirth, spontaneous abortion or elective termination, but excluding those lost-to-follow-up.

Due to the observational nature of the study, the above crude estimate of RR will be further adjusted for potential confounders, provided that there are sufficient number of events. A complete list of potential confounders will be provided in a separate table for each outcome prior to the final analysis, based on scientific knowledge including literature review. In addition, all of the following three criteria will be applied in

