to when women would typically enroll in the study. However, based on expected gestational timing of enrollment, spontaneous abortion rates in late first trimester and early second trimester will be analyzable. Further, measurement of a rare outcome may also limit the ability to adjust for potential confounders in multivariable analyses. Where possible due to sufficient events, a propensity score is planned to include relevant confounders.

A bias of this study might be associated with right truncation or censoring. This occurs when pregnancies end the follow-up before the outcome is known (censoring), or with unknown outcomes (truncation). Since pathology is rarely available for spontaneous abortions and terminations for social reasons, most cohorts consider the prevalence of malformations in livebirths rather than the cumulative incidence over gestation. Failure to include defects detected among terminations can underestimate the incidence of malformations and decrease power but, if the missingness is random with respect to exposure, the relative risk for malformations will be unbiased. Additionally, for other outcomes that are also dependent on timing of enrollment in relation to the outcome occurrence (e.g. elective termination and ectopic/molar pregnancy) there may be incomplete data. The dysmorphology exam for minor birth defects may not be performed consistently across all infants and thus there may be missing data for some infants. Medical records may also not be available for all women or infants and there could be missing data from these sources as well. Efforts will be made to enroll a disease comparison group that is of similar disease severity however, there could be differences between the cohorts that may not be able to be adjusted or accounted for due to the nature and collection of the data.

Strengths of the study design are the ability to build on the referral network of OTIS member services across the U.S. and Canada to identify belimumab-exposed pregnancies as well as appropriate comparison group pregnancies, the OTIS research groups' track record of excellent subject retention (<5% lost to follow-up) [[Chambers, 2010](#); [Chambers, 2016](#); [Chambers, 2019b](#)]. In addition, the study design allows for appropriate comparison to a treated disease group, and for appropriate attention to confounding or effect modification.

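### Table 2 limits the secondary major birth defect analysis to pregnancies with a live birth, against its own heading and Section 8.7.1

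*Protocol*

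**What the plan says.** The major birth defect row of Table 2 (Protocol Section 8.3.2) describes a primary and a secondary analysis.

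- The secondary analysis has the heading "Secondary analysis (among all pregnancies excluding lost-to-follow up".
- The Cohort 1 endpoint under that heading is "At least one malformed infant or fetus in an individual pregnancy among pregnancies ending in at least one live birth with exposure to belimumab".
- The Cohort 2 endpoint is "At least one malformed infant or fetus in an individual pregnancy among pregnancies ending in at least one live birth with no exposure to belimumab".
- The Denominator column for the row has one entry, "Pregnancies ending in live births".

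Section 8.7.1 sets the primary comparison "between Cohort 1 and Cohort 2 among pregnancies resulting in at least one live born infant". It then adds: "The same analysis will be repeated using the second numerator and denominator encompassing pregnancies ending in at least one live births, stillbirth, spontaneous abortion". That sentence goes on to include elective terminations and to leave out women lost to follow-up.

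Section 8.9 gives the reason for looking beyond live births: "Failure to include defects detected among terminations can underestimate the incidence of malformations and decrease power". The same sentence adds that the relative risk stays unbiased if the missingness is random with respect to exposure.

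**The concern.** One analysis is given two incompatible populations. The heading in Table 2 and Section 8.7.1 describe all pregnancies with a known outcome. The two endpoint cells and the Denominator column describe live-birth pregnancies, which is already the primary population.

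Table 2 is not background text. Section 8.4 refers to it for the definitions used to classify outcomes, and Section 8.6.1 says that staff code outcomes from the protocol's definitions. An analyst who programs from the endpoint cells would repeat the primary analysis almost unchanged. Malformed fetuses in pregnancies that end in stillbirth, spontaneous abortion or termination would not enter any comparative birth defect analysis. Section 8.5 describes the study as an early warning system for a major teratogen, so those cases are relevant to its purpose.

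**Working it through.** **1. The definitions side by side**

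| Source | Population for the secondary analysis |
|---|---|
| Table 2, heading | All pregnancies, less lost to follow-up |
| Table 2, Cohort 1 and Cohort 2 endpoints | At least one live birth |
| Table 2, Denominator column | Live births only |
| Section 8.7.1 | Live birth, stillbirth, spontaneous abortion or elective termination, less lost to follow-up |

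The secondary numerator names an infant or a fetus, where the primary names an infant. Within live-birth pregnancies that wording can add, at most, a malformed fetus whose co-twin is born alive. Every malformed fetus in a pregnancy without a live birth is left out.

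**2. Reproducing the plan's denominators**

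Inputs from Section 8.5: 200 enrolled per cohort; spontaneous plus elective abortion 10% (base) or 15% (conservative); loss to follow-up 5%.

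Live-birth pregnancies = 200 × (1 − abortion rate − loss rate).

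- Base: 200 × (1 − 0.10 − 0.05) = 170
- Conservative: 200 × (1 − 0.15 − 0.05) = 160

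Both match the protocol.

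**3. The Section 8.7.1 denominator and the gap**

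All outcomes less lost to follow-up = 200 × (1 − 0.05) = 190 per cohort.

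- Base: 190 − 170 = 20 left out; 20/190 = 10.5%
- Conservative: 190 − 160 = 30 left out; 30/190 = 15.8%

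Section 8.5 makes no separate allowance for stillbirth, so these 20 to 30 are spontaneous and elective abortions as planned there.

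**4. What the omission could hide (illustration only)**

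The defect rates in pregnancies without a live birth are assumptions; the protocol gives none. Assume 5% defects among live-birth pregnancies in both cohorts (one of the background rates in Table 4) and 5% detected defects among unexposed pregnancies without a live birth. Vary the exposed rate. Both denominators are 190, so RR = exposed cases / unexposed cases.

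| Exposed rate, no live birth | 20 such pregnancies | 30 such pregnancies |
|---|---|---|
| 5% | 9.5 / 9.5 = 1.00 | 9.5 / 9.5 = 1.00 |
| 25% | 13.5 / 9.5 = 1.42 | 15.5 / 9.5 = 1.63 |
| 50% | 18.5 / 9.5 = 1.95 | 23 / 9.5 = 2.42 |

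For example, with 20 such pregnancies and a 25% rate, exposed cases = 0.05 × 170 + 0.25 × 20 = 13.5. Under the Table 2 wording the RR is 1.00 in every row.

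**5. Precision**

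Take 8 live-birth cases per cohort (5% of 160) and assume 4 further exposed cases and no further unexposed cases. Then RR = 12/8 = 1.5. The standard error of log RR is √(1/12 + 1/8 − 2/190) = 0.445, so the 95% CI is 1.5 × exp(±1.96 × 0.445), about 0.6 to 3.6. A shift of that size would be inconclusive.

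**The case against.** The best defence is that the intended population is not really in doubt. The heading states it, the numerator mentions a fetus, and Section 8.7.1 lists the outcomes in full. Section 8.7.3 says that the final analyses follow Sections 8.7.1 and 8.7.2, and a SAP must be finalized before any analysis. The live-birth clause looks carried over from the primary endpoint just above it. This stands, and it lowers the severity. It does not remove the contradiction, because the live-birth limit appears three times in the row that defines the primary outcome.

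A reader might draw stronger conclusions that the documents do not support:

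- **That the live-birth relative risk is biased downward.** This needs omitted defects to differ by exposure. The protocol does not say that exposed women have more surveillance or more terminations for anomaly, and Section 8.9 states the random-missingness condition under which the RR is unbiased.
- **That this analysis is the only check on such selection.** Table 2 compares stillbirth and elective termination by cohort, with reasons for termination classed as medical or social. Section 8.7.1 stratifies by prenatal diagnostic testing before enrollment, and Section 8.7.2 by abnormal findings on such testing. These are partial checks. None of them counts defects in pregnancies without a live birth, but they exist.
- **That the study's conclusion would change.** The RR shifts shown depend on assumed rates. Section 8.9 also notes that pathology is rarely available for spontaneous abortions and social terminations, so fewer than 20 to 30 pregnancies per cohort could supply a detected defect.
- **That the plan must add reporting of fetal examinations, or a denominator restricted to known malformation status.** The contradiction requires neither.

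**Conclusion.** The inconsistency is real and limited; it is a should-fix. Two endpoint cells and the Denominator column in Table 2 contradict the heading of the same analysis and Section 8.7.1. Followed literally, they exclude 20 to 30 of 190 pregnancies per cohort (10.5% to 15.8%) and reduce the secondary analysis to a near duplicate of the primary. Those counts rest on the enrollment, abortion and follow-up rates in Section 8.5.

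The documented consequence is the one in Section 8.9: possible underestimation of incidence and loss of power. Bias in the relative risk is conditional on differential omission, and its size cannot be derived from the protocol. The primary analysis and the Table 4 effect sizes use the live-birth population by design and are unaffected.

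**What to change.** In the major birth defect row of Table 2, in both secondary endpoint cells, replace the live-birth clause with the Section 8.7.1 population: every pregnancy ending in live birth, stillbirth, spontaneous abortion or elective termination, with those lost to follow-up excluded. Keep the exposure wording of each cell. In the Denominator column, label the present entry as primary and add this population as the secondary denominator.

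The cost is a change to three table cells, best made before the SAP is finalized. It alters no sample size and no primary analysis, and it adds no analysis beyond the one that Section 8.7.1 already plans.
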